All measurable disease must be documented at Screening by physical examination, laboratory testing, and CT scan (or MRI in the case CT is medically contraindicated). During the study, clinical disease assessments will take place at Week 24, Week 36, and Week 48. To confirm the response, a CT scan will be performed at Week 48.

Minimal Residual Disease (MRD):

A peripheral blood specimen will be collected from all subjects at Week 1 Day 1 (baseline), Week 24 and Week 48 to determine the level of minimal residual disease. When confirming a CR/CRi status per 2008 Modified IWCLL NCI-WG criteria with a bone marrow biopsy and aspirate, MRD assessment of the BM aspirate should also be performed. The level of MRD and MRD negativity will be assessed. MRD negativity in the 2008 Modified IWCLL NCI-WG criteria is defined as the presence of less than one CLL cell per 10,000 leukocytes (or below 10^{-4}).

Pharmacokinetics:

A single pharmacokinetic (PK) blood sample will be collected from each subject and analyzed for plasma venetoclax concentration.

Safety:

Adverse event monitoring, vital signs, physical examination, and laboratory assessments will be evaluated.

The study analyses will be descriptive. All subjects participating in the study who received at least one dose of venetoclax will be included in the analyses unless otherwise noted in the separate, statistical analysis plan (SAP).

Statistical Methods (Continued):

Efficacy:

The following efficacy endpoints will be analyzed: Complete Remission rate (CR + CRi), Overall Response Rate (ORR), Duration of Overall Response (DOR), Duration of Progression-Free Survival (PFS) and Overall Survival (OS):

Complete Remission Rate (CR) and Complete Remission with Incomplete Marrow Recovery (CRi)

Defined as the proportion of subjects who achieved a CR or CRi (all subjects and previously BCRi treated subjects).

Overall Response Rate (ORR)

Defined as the proportion of subjects with an overall response (complete remission plus partial remission).

Duration of Response (DOR)

Defined as the number of days from the date of first response (per the 2008 Modified IWCLL NCI-WG criteria) to the date of disease progression. All disease progression will be included regardless whether the event occurred while the subject was taking venetoclax or had previously discontinued venetoclax.

Time to Progression (TTP)

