A laboratory test value that requires a subject to be discontinued from the study, requires a subject to receive treatment, meets protocol specific criteria (see Section 6.1.8 regarding toxicity management), or if the Investigator considers clinically significant will be recorded as an adverse event.

NOTE: Starting with Week 8/Day 1, clinical laboratory tests may be collected within 72 hours prior to the scheduled visit.

Disease Assessments (2008 Modified IWCLL NCI-WG Criteria)

All measurable disease must be documented at Screening (baseline), prior to the first dose of venetoclax, for all subjects based on the analysis of clinical laboratory tests (hematology), disease assessment physical examination, contrast-enhanced CT scan of involved neck, chest, abdomen and pelvis (or MRI, if CT scan with contrast is medically contraindicated). Bone marrow examinations at screening are not required but results will be recorded if available.

For all subjects, clinical response will be assessed by the investigator at Week 24, Week 36 and Week 48. Disease response will be based on the analysis of clinical laboratory tests and a disease assessment physical examination. To confirm the response, a contrast-enhanced CT scan (or MRI, if CT scan with contrast is medically contraindicated) will be performed at Week 48 for all subjects. Subjects will be evaluated using the 2008 Modified IWCLL NCI-WG criteria for Tumor Response with the addition of CT imaging (or MRI).

For determination of complete remission (CR), the CT scan and bone marrow are required to be negative, per the IWCLL NCI-WG criteria. It is recommended that the CT scan is performed first; if it does confirm a clinical response, then a bone marrow biopsy will be obtained. If a CT scan is performed and does not confirm a clinical response, a bone marrow biopsy should not be obtained.

If a subject exhibits clinical signs of possible disease progression (i.e., increased or *de novo* enlargement of liver, spleen or lymph nodes on physical examination) without an increase in lymphocytes meeting the progression of disease criteria, then additional assessments including contrast-enhanced CT scan and/or bone marrow can be performed to confirm or rule out disease progression.

The same method of assessment and the same technique should be used to characterize each identified and reported lesion at baseline and during follow-up.

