- Absence of lymphadenopathy (nodes > 15 mm in longest diameter or any extra nodal disease) by physical examination and CT scan
- No hepatomegaly or splenomegaly by physical examination (as determined by measurement below the relevant costal margin)
- Absence of disease or constitutional symptoms (B symptoms: unexplained fevers > 38°C or 100.4°F, drenching night sweats, > 10% body mass weight loss in the preceding 6 months)
- Blood counts above the following laboratory values:
 - Neutrophils > $1.5 \times 10^9/L$ [1500/ μL] (without the need for exogenous growth factors)
 - Platelets > $100 \times 10^9/L$ [100,000/ μL] (without the need for platelet transfusion or exogenous growth factors)
 - Hemoglobin > 110 g/L [11 g/dL] (without the need for blood transfusions or exogenous erythropoietin)
- Bone marrow at least normocellular for age, < 30% of nucleated cells being lymphocytes. Lymphoid nodules should be absent. Bone marrow aspirate and biopsy should be performed after CR/CRi has been achieved. If the bone marrow is hypocellular, a repeat determination should be made in 4 weeks or when peripheral blood counts have recovered. A marrow biopsy should be compared to a pre-treatment marrow if available. Subjects who are otherwise

in a complete remission, but bone marrow nodules can be identified histologically should be considered to be nodular PR (nPR). Immunohistochemistry (IHC) should be performed to define whether these nodules are composed of primarily T cells or lymphocytes other than CLL cells, or CLL cells.

Complete Remission with Incomplete Marrow Recovery (CRi)

Subjects who fulfill the criteria for CR (including bone marrow) but who have persistent cytopenia (anemia or thrombocytopenia or neutropenia) apparently unrelated to CLL but related to drug toxicity will be considered CRi. The marrow evaluation described above should be performed with scrutiny and not show any clonal infiltrate.

Partial Remission (PR)

To be considered a PR at least 2 of the following must be met:

- $\geq 50\%$ decrease in peripheral blood lymphocyte count from the pretreatment baseline value.
- $\geq 50\%$ reduction in lymphadenopathy.
- $\geq 50\%$ reduction in the size of the liver and/or spleen (if abnormal prior to therapy).

In addition at least **one** of the following criteria must be met:

- Neutrophils $> 1,500/\mu\text{L}$ or $\geq 50\%$ improvement over baseline.
- Platelets $> 100,000/\mu\text{L}$ or $\geq 50\%$ improvement over baseline.

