 - i. For all subjects, on the day of Week 1 Day 1, before dosing, the chemistry/hematology panel should be collected. The results of the labs drawn on Week 1 Day 1 need to be reviewed prior to dosing **IF** an additional lab within 72 hours of the initial dose at Week 1 Day 1 was not drawn **AND** reviewed.
 - j. For all subjects, the chemistry/hematology panel should be monitored at 6 to 8 hours and at 24 hours after the first dose of venetoclax (20 mg) and after the first dose increase (50 mg). The next venetoclax doses should not be administered until the 24 hour lab results have been evaluated. Electrolyte abnormalities should be corrected promptly.
Note: There is a ± 2 hour window around the 24 hour lab draw.
 - k. For all subjects, within 72 hours of each subsequent dose increase, the chemistry/hematology panel should be repeated. The results should be reviewed prior to dose increasing.
 - l. Prior to dosing, on the day of each subsequent dose increase, the chemistry/hematology panel is required. The results of the labs drawn on Day 1 of each dose increase need to be reviewed prior to dosing **IF** additional labs within 72 hours of the dose increase were not drawn **AND** reviewed.
 - m. For subjects who continue to be at risk of TLS, the same lab monitoring schedule of 6 to 8 hour and 24-hr post dose should be followed at the subsequent dose increases.
Note: There is a ± 2 hour window around the 24 hour lab draw.
-

- n. All measurable disease must be documented at Screening by laboratory testing, physical examination and CT scans (or MRI if CT is medically contraindicated); bone marrow examinations are not required at screening but results will be recorded if available. All baseline evaluations should be performed as closely as possible to the beginning of treatment. For all subsequent disease assessments, disease response will be assessed by the investigator based on the analysis of clinical laboratory tests (hematology) and a complete physical examination at Week 24, Week 36 and Week 48.

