10.1.1 Definitions for Efficacy Endpoints

Complete Remission Rate (CR + CRi)

Complete response rate, complete remission (CR) or complete remission with incomplete marrow recovery (CRi), will be defined as the proportion of subjects per the 2008 Modified IWCLL NCI-WG criteria as assessed by investigator using the best response at any time during the study. In addition, the 95% confidence interval for complete response rate (CR) rate based on the binomial distribution (Clopper-Pearson exact method) will be provided. Subjects who do not achieve a CR or CRi will be considered to be non-responders in the calculation of complete response rate.

Overall Response Rate (ORR)

ORR (CR + CRi + nPR + PR) will be defined as the proportion of subjects who achieved complete remission (CR), complete remission with incomplete marrow recovery (CRi), nodular partial remission (nPR), or confirmed partial remission (PR) based on the 2008 Modified IWCLL NCI-WG criteria as assessed by investigator using the best response at any time during the study. Confirmatory PR response will be determined by not less than 49 days from the first PR was observed. The corresponding exact 95% confidence interval for the proportion (Clopper-Pearson exact method) will be constructed. Subjects who do not respond will be considered non-responders.

Duration of Response (DOR)

The DOR for a given subject will be defined as the number of days from the day the criteria are met for CR, CRi, nPR, or confirmed PR (whichever is recorded first) to the earliest date that progressive disease (PD) is objectively documented (radiographic or clinical) or death (i.e., $DOR = PD/death/censoring\ date - earliest\ CR/CRi/nPR/PR\ date + 1\ day$). For subjects who have a PR before CR, CRi, or nPR in subsequent visits, the DOR is computed from the earliest PR. If a subject is still responding then the subject's data will be censored at the date of the last available disease assessment prior to the data cutoff date. Only subjects with the iWCLL response criteria will be included in the analysis of DOR. The distribution of the duration of overall response will be estimated using the Kaplan-Meier methodology. Median duration of response will be calculated and the corresponding 95% confidence interval will be presented.

Time to Progression (TTP)

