10.2.2 Secondary Efficacy Analyses

ORR will be assessed as the proportion of subjects with an overall response (CR + CRi + nPR + PR) based on the IWCLL NCI-WG criteria. The ninety-five percent (95%) confidence interval based on the Clopper-Pearson exact method for binomial distribution will be constructed for the calculated ORR rate.

DOR, TTP, PFS, and OS will be analyzed by Kaplan-Meier methodology using data for all subjects defined in Section 5.1.1. Median time of each endpoint will be calculated and 95% confidence interval for median time of each endpoint will be presented.

The analyses of ORR, DOR, TTP, PFS, and OS will be performed on ITT, ITT-BN, and ITT-BE population.

The complete remission (CR + CRi) rate in will be assessed based on the 2008 Modified IWCLL NCI-WG criteria for ITT and ITT-BE population. The ninety-five percent (95%) confidence interval based on binomial distribution will be constructed for the calculated complete remission rate.

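### SAP 10.1.1 requires PR to be confirmed at least 49 days later, which the protocol does not state and the visit schedule cannot deliver for a PR first seen at Week 48

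*SAP*

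**What the plan says.** **Confirmed PR.** SAP 10.1.1 builds ORR from CR, CRi, nPR "or confirmed partial remission (PR) based on the 2008 Modified IWCLL NCI-WG criteria as assessed by investigator". It then sets the interval: "Confirmatory PR response will be determined by not less than 49 days from the first PR was observed". The DOR definition in the same section also starts from CR, CRi, nPR or confirmed PR, whichever comes first.

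**PR with no stated confirmation.** SAP 10.2.2 says "ORR will be assessed as the proportion of subjects with an overall response (CR + CRi + nPR + PR" and does not mention confirmation. Protocol 8.1.2.2 uses the same wording. The protocol synopsis has "Defined as the proportion of subjects with an overall response (complete remission plus partial remission". The printed response criteria in Protocol 5.3.3.1 begin "To be considered a PR at least 2 of the following must be met" and go on to list thresholds. Neither the list nor Table 5 gives a minimum duration or a repeat assessment for PR.

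**Schedule.** Protocol 5.3.1.1 states: "For all subjects, clinical response will be assessed by the investigator at Week 24, Week 36 and Week 48". Appendix D, footnote n, gives the same three visits. After Week 48, Appendix D continues physical examination and hematology every 12 weeks but schedules no disease assessment or CT. For subjects in PR at Week 48, Protocol 5.3.1.1 permits, but does not require, a further CT and marrow up to Week 108. Its stated purpose is to confirm CR.

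**The concern.** The SAP adds a condition that the protocol does not state, and gives no reason for it. The planned visits can meet the condition for a PR first seen at the first two assessments but not for one first seen at the last. Week 48 is also the only post-baseline visit with a mandatory CT, so the PRs that cannot be confirmed on schedule are those first documented at the visit with the fullest scheduled imaging.

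ORR and DOR are among the key secondary endpoints in Protocol 8.1.2.2. If late PRs are counted as non-response because no visit follows, reported ORR is too low for a reason unrelated to the drug. ORR also appears in the subgroup forest plot (SAP 10.4), so the same loss carries into it.

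**Working it through.** The documents state no expected value, sample size or power for ORR, so there is no planned figure to reproduce. The check is calendar arithmetic followed by an illustration of size.

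**Step 1. Can a PR first seen at Week 24 or 36 be confirmed?** SAP Table 2 gives nominal days 162 (Week 24), 246 (Week 36) and 330 (Week 48).

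- Gaps: 246 − 162 = 84 days and 330 − 246 = 84 days.
- Windows: visits may move by 2 days from Week 8 on (Protocol 5.1). Disease assessments may be done about 7 days before the visit (Protocol 5.3.1.1).
- Shortest gap: 84 − 2 − 7 = 75 days. If the 2-day window is also added to the early side, 84 − 2 − 9 = 73 days.

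Both exceed 49 days, so the next scheduled assessment can confirm these PRs.

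**Step 2. Can a PR first seen at Week 48 be confirmed?** The earliest qualifying day is 330 + 49 = 379. No disease assessment is scheduled on or after that day. Under Protocol 8.1.3 the efficacy cutoff is the last enrolled subject's Week 48 assessment, or the date when all subjects are off drug if that is earlier. Subjects enrolled early may have more than 49 days of further data before the cutoff. The last to reach Week 48 have none.

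**Step 3. How large could the loss be?** Let f be the share of PRs first seen at Week 48. The documents do not give it, so 2% to 20% is an assumption. If none of these PRs is rescued by a later recorded assessment:

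loss in ORR = f × (ORR − CR/CRi rate)

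The rates come from the earlier monotherapy study in Protocol 3.0: ORR 75.0% with CR/CRi 32.1% in dose escalation, and ORR 81.7% with CR/CRi 11.7% in safety expansion. The PR shares are 75.0 − 32.1 = 42.9 points and 81.7 − 11.7 = 70.0 points.

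| f (assumed) | Loss, PR share 42.9 | Loss, PR share 70.0 |
|---|---|---|
| 2% | 0.9 points | 1.4 points |
| 5% | 2.1 points | 3.5 points |
| 10% | 4.3 points | 7.0 points |
| 20% | 8.6 points | 14.0 points |

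The difference treats all non-CR/CRi responses as PR. Any nPR among them needs no confirmation under the SAP, so the losses are slightly overstated to that extent.

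For scale, the half-width of a 95% interval at ORR 75% with 250 subjects is 1.96 × √(0.75 × 0.25 / 250) = 5.4 points by the normal approximation.

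**Step 4. DOR.** The SAP formula adds 1 day to the difference between dates. A subject whose only PR is at Week 48, with no later assessment, would be censored with a DOR of 1 day. That adds almost nothing to the Kaplan-Meier curve, so the effect on DOR is mainly on who enters the analysis.

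**The case against.** **Two ORR rules within the SAP?** A reader might infer that 10.1.1 and 10.2.2 contradict each other and that the result depends on which is programmed. The documents do not establish this. Section 10.1.1 is the definitions section and attaches the short label CR + CRi + nPR + PR to the confirmed definition, so 10.2.2 can be read as using that label. For DOR, 10.2.2 offers no competing definition. The firm difference is between SAP and protocol.

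**Legitimate elaboration?** Protocol 8.1 leaves detailed analysis descriptions to the SAP, and both documents refer to published response criteria that cannot be consulted here. The protocol's position therefore rests on what it prints, which contains no confirmation rule. Even if confirmation is accepted as elaboration, the Week 48 gap remains.

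**Is every Week 48 PR lost?** That stronger reading fails. The SAP takes the best response over the whole study and uses data up to the cutoff. An optional CT and marrow, a standard-of-care scan, a routine 12-weekly examination with hematology, or a later CR or CRi could rescue some subjects. But these are optional or are not designated disease assessments, and the SAP gives no rule for using them to confirm PR.

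**Is a Week 24 PR that ends before Week 36 also a scheduling bias?** No. Screening out short-lived responses is what confirmation is for.

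**Does the Week 48 CT make confirmation unnecessary?** Not for everyone. A subject in PR at Week 24 who leaves before Week 48 has no scheduled CT, because the assessments at Weeks 24 and 36 rest on examination and laboratory tests.

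**Stakes.** SAP 10.1 plans no efficacy testing, so no hypothesis test turns on this point.

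**Conclusion.** The concern holds in a limited form. The SAP adds a PR confirmation requirement that the protocol does not state. For a PR first seen at Week 48, the schedule provides no assessment that could meet it. Such a subject counts as a non-responder unless unscheduled or optional data happen to be recorded in time, so the bias in ORR is downward.

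The documents do not give its size. The range of about 1 to 14 points rests on three assumptions: 2% to 20% of PRs first appear at Week 48, the earlier-study response rates apply here, and no such PR is rescued. The upper part of the range exceeds the sampling error of the estimate, and the lower part is minor. PRs first seen at Week 24 or 36 can be confirmed. The primary CR + CRi rate is unaffected. This should be settled in the SAP, but it does not threaten the trial's main conclusion.

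**What to change.** - In SAP 10.1.1 and 10.2.2, use the Protocol 8.1.2.2 definition of ORR (CR + CRi + nPR + PR), and take the same set of responders into DOR.
- Report ORR with PR confirmed at 49 days or more as a sensitivity analysis. Show PRs first seen at Week 48 in their own category, labelled as not confirmable on schedule, rather than merging them silently with non-responders.

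The cost is SAP wording and one additional table, with no new data collection. The downside is that ORR by the protocol definition will include some short-lived PRs and some never supported by CT. The confirmed sensitivity analysis shows how much depends on PRs that were not confirmed.

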5.3.3.1 Primary Variables

For disease assessments, response will be assessed by the investigator based on analysis of clinical laboratory tests (hematology laboratory values), disease assessment physical examination, CT scan including neck, chest, abdomen, and pelvis (or MRI if CT with contrast is medically contraindicated); bone marrow aspirate are not required but results will be recorded if available. Subjects will be evaluated against the 2008 Modified

IWCLL NCI-WG Criteria for Tumor Response⁴⁶ with CT imaging (or MRI). A BM sample assessment is required to confirm CR.

At screening (baseline), all measurable disease must be documented by laboratory testing (hematologic status), physical examination, and CT scan. All baseline evaluations should be performed as closely as possible to the beginning of treatment and not more than 4 weeks before the beginning of the treatment with the exception of the CT scan (or MRI) which will be accepted if previously performed within 35 days prior to study drug initiation. During the study, subjects will have a disease assessment at Week 24, Week 36 and Week 48. To confirm the response, a CT scan will be performed at Week 48 on all subjects. For subjects with CR as response at Week 48, a BM sample is required to confirm the response.

Methods of Measurement

Disease response and progression will be assessed by analysis of peripheral blood, clinical examination, radiographic scans and bone marrow aspirate and biopsy.

The same method of assessment and the same technique should be used to characterize each identified and reported lesion at baseline and during follow-up.

Details on the analysis of peripheral blood required to assess response are provided in Section [5.3.1.2](#).

A full disease assessment physical examination should be performed to assess the extent of disease involvement. Physical examinations should include the evaluation of the presence and degree of enlarged lymph nodes in two dimension (cervical, supraclavicular, axillary, inguinal and femoral nodes), hepatomegaly, and splenomegaly. These should be noted on all examinations irrespective of being present or absent. All measurements should be taken and recorded in metric notation using a ruler or calipers. Clinical lesions will only be considered measurable when they are superficial (e.g., palpable lymph nodes). The diameter, in two planes, of the largest palpable nodes in each of the

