Progression-free survival (PFS) will be defined as the number of days from the date of first dose to the date of earliest disease progression or death. All disease progression will be included regardless whether the event occurred while the subject was taking the study drug or had previously discontinued the study drug. If the subject does not experience disease progression or death, then the data will be censored at the date of last disease

assessment. Data for subjects who receive non-protocol CLL therapy prior to disease progression will be censored at the last disease assessment prior to receiving non-protocol therapy. Data for subjects without any disease assessments performed after the baseline visit will be censored at the time of enrollment plus 1 day. PFS will be analyzed by Kaplan-Meier methodology using data for all subjects enrolled. Median time PFS will be calculated and 95% confidence interval for median time PFS will be presented.

Overall survival (OS) will be defined as number of days from the date of first dose to the date of death for all dosed subjects. For subjects who did not die, their data will be censored at the date of last study visit or the last known date to be alive, whichever is later. OS will be analyzed by Kaplan-Meier methodology using data from all enrolled subjects. Median time survival will be estimated and 95% confidence interval for the median time survival will be presented.

The CR rate (CR + CRi) in previously treated BCRi subjects will be assessed based on the 2008 Modified IWCLL NCI-WG criteria. The ninety-five percent (95%) confidence interval based on binomial distribution will be constructed for the calculated CR rate.

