Time to progression for a given subject will be defined as the number of days from the date the subject started venetoclax to the date of earliest PD (radiographic or clinical) (i.e., $TTP = PD/censoring\ date - first\ dose\ date + 1\ day$). If the subject does not experience disease progression then the subject's data will be censored at the date of the last available disease assessment prior to the data cutoff date. If a subject does not have

any post baseline disease assessments, the data will be censored at the first dose date plus 1 day. The distribution of the time to progression will be estimated using Kaplan-Meier methodology. Median time to progression and the corresponding 95% confidence interval will be estimated.

Progression Free Survival (PFS)

Progression-free survival (PFS) will be defined as the number of days from the date of first dose of venetoclax to the date of earliest PD (radiographic or clinical) or death (i.e., $PFS = PD/death/censoring\ date - first\ dose\ date + 1\ day$). If the subject does not experience disease progression or death then the subject's data will be censored at the date of the last available disease assessment prior to the data cutoff date. If a subject does not have any post baseline tumor assessment or clinical assessment for progression, the data will be censored at the date of first dose plus 1 day. Progression-free survival will be analyzed by Kaplan-Meier methodology. Median duration of PFS will be calculated and 95% confidence interval for median duration of PFS will be presented.

Overall Survival (OS)

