Overall survival (time to death) for a given subject will be defined as the number of days from the first dose date of venetoclax to the date of the subject's death (i.e., $OS = death/censoring\ date - first\ dose\ date + 1\ day$). All events of death will be included, regardless of whether the event occurred while the subject was still taking any study drug, or after the subject discontinued any study drug. If a subject has not died, then the data will be censored at the date when the subject was last known to be alive prior to the cutoff date. The date of the last known to be alive will be determined by selecting the last available date of the following study procedures for a subject: study visit/contact date, tumor assessment, clinical disease progression, physical examination, vital signs assessment, clinical laboratory collection, study drug, adverse event assessment, concomitant medication assessment, drug or study completion, survival visit, and post treatment therapy assessment. The distribution of the time to death will be estimated

using Kaplan-Meier methodology. Median survival time and the corresponding 95% confidence interval will be estimated.

Minimal Residual Disease (MRD) Response Rate

The rate of MRD response in CLL subjects will be defined as the proportion of CLL subjects who achieved MRD negative status with less than one CLL cell per 10,000 leukocytes (or below 10^{-4}). All subjects with an MRD assessment will be included in the denominator for the calculation of MRD response rate. Minimal residual disease response will be summarized by categories: MRD negative, MRD positive, or MRD unknown/missing. The 95% confidence intervals based on the binomial distribution (Clopper-Pearson exact method) will be provided.

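### As worded, the PFS censoring rule for subjects with no post-baseline assessment makes no exception for deaths, which conflicts with the definition of death as a PFS event

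*SAP*

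**What the plan says.** SAP 10.1.1 runs PFS from first dose "to the date of earliest PD (radiographic or clinical) or death". Two censoring sentences follow.

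- The general one is conditional: "If the subject does not experience disease progression or death then the subject's data will be censored", at the last available disease assessment before the cutoff.
- The second covers a subject with no post-baseline "tumor assessment or clinical assessment for progression, the data will be censored at the date of first dose plus 1 day". It carries no condition about progression or death.

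Protocol 8.1.2.2 also counts death as a PFS event and has a similar unconditional sentence: "Data for subjects without any disease assessments performed after the baseline visit will be censored at the time of enrollment plus 1 day".

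On timing, protocol 5.3.1.1 states that "clinical response will be assessed by the investigator at Week 24, Week 36 and Week 48". Before Week 24, if there are clinical signs of possible progression without a qualifying rise in lymphocytes, "then additional assessments including contrast-enhanced CT scan and/or bone marrow can be performed to confirm or rule out disease progression".

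For OS, by contrast, SAP 10.1.1 is explicit: "All events of death will be included, regardless of whether the event occurred while the subject was still taking any study drug", or afterwards. PFS has no such sentence for deaths.

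**The concern.** A subject who dies without ever having been assessed for progression meets both the event definition and the second censoring rule, and neither document says which prevails. The wording parallels the TTP rule just above it in SAP 10.1.1. There it does no harm, because death is not a TTP event. For PFS it does matter.

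The SAP is meant to guide programming (SAP 3.0). A programmer who applies the no-assessment rule before looking for events would turn such deaths into censorings near time zero. Those subjects leave the risk set before they can lower the curve, so the error runs in one direction: PFS looks better than it was.

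**Working it through.** The documents state no PFS event count, median or power, so there is no figure to reproduce. The check is first of wording, then an illustration of size.

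**1. What the rule does to one subject.** SAP 10.1.1 computes PFS as end date minus first dose date plus 1 day. Take a subject who dies in Week 10 with no qualifying assessment:

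- Event definition: an event on the date of death.
- No-assessment rule: (first dose + 1) − first dose + 1 = 2 days, censored.

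**2. Whether another section resolves it.** SAP 6.4 deals with missing progression, death and last-alive dates and restores no deaths. The protocol's PFS sentence on events after stopping drug covers progression only. The OS sentence applies to OS alone.

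**3. Who is exposed.** The first scheduled post-baseline disease assessment is Week 24, nominal day 162 in SAP Table 2 (23 × 7 + 1 = 162). Deaths before then in unassessed subjects fall under the rule. So do later deaths, found in telephone follow-up, among subjects who stopped before Week 24 without an assessment. A death after an unscheduled scan or other qualifying assessment stays an event.

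**4. The two documents differ.** The SAP trigger is absence of a tumor or clinical assessment for progression; the protocol trigger is absence of a disease assessment. The SAP date is first dose plus 1 day; the protocol date is enrollment plus 1 day. Protocol 8.1 defines enrollment as the date the IRT gave a subject number, and protocol 5.5.3 allocates numbers at Screening. The protocol's censoring date could therefore precede first dose, from which PFS is counted.

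**5. Illustration of size.** Inputs: N = 250 (SAP 4.2) or 190 BCRi-naive subjects (SAP 4.3). The number d of unassessed deaths before Week 24 is assumed to be 5, 10 or 15, because the documents give no rate. It is further assumed that there is no other event or censoring before Week 24. Kaplan-Meier PFS just before Week 24 is then 1 − d/N with the deaths counted, and 100% as worded.

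| d | N = 250, counted | N = 190, counted | As worded |
|---|---|---|---|
| 5 | 98.0% | 97.4% | 100% |
| 10 | 96.0% | 94.7% | 100% |
| 15 | 94.0% | 92.1% | 100% |

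Under the same assumptions the later curve is too high by the factor 1/(1 − d/N). For N = 250 that is 1/0.98 = 1.020 to 1/0.94 = 1.064.

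**6. The planned output is a median.** Suppose a constant hazard after Week 24, with the as-worded curve reaching 50% m months after Week 24. Counting the deaths brings that point forward by −m × log2(1 − d/N) months. With N = 250:

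- m = 24, d = 5: 24 × 0.0291 = 0.7 months.
- m = 36, d = 15: 36 × 0.0893 = 3.2 months.

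Both values of m are assumptions.

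**The case against.** The strongest reply is that the context already settles it. The event definition and the PFS formula both include death, and the general censoring sentence is limited to subjects without progression or death. The disputed sentence can be read as supplying a date when that general sentence has no assessment date to use. This may well be the intent. But the text does not carry the condition over, so the reply makes the conflict easy to repair without removing it.

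A reader might infer that almost every death before Week 24 would be lost. The documents do not support that. The SAP term, a clinical assessment for progression, is undefined and looks broader than a scheduled disease assessment. Appendix D of the protocol has physical examinations and hematology on Day 1 of Weeks 1 to 5 and at Weeks 8, 12, 16 and 20, and progression under protocol 5.3.3.2 can be shown by lymphocyte counts, cytopenia, nodes or organ size. If those visits qualify, few deaths are affected. Against that, protocol 5.3.1.1 lets examinations at other visits be symptom-directed and limited in scope, so it is not clear that they do qualify.

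A reader might also infer a known inflation of PFS, with many early deaths from tumor lysis or rapid progression. That is not supported either. No early death rate is given. Protocol 3.0 reports no fatal tumor lysis event in its analysis after the revised titration and prophylaxis. A subject with documented progression has already been assessed and already has an event. Progression documented before Week 24 would also keep the literal curve below 100%.

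Finally, PFS is secondary, and SAP 10.1 plans no testing of efficacy endpoints. Early deaths stay visible in OS and in the death tables of SAP 11.3. This stands, and it limits the consequence.

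**Conclusion.** The wording conflict is real and present in both documents: death is a PFS event, yet the no-assessment rule has no exception for subjects who died. Applied literally, it drops deaths in subjects never assessed for progression and biases PFS upward. It does not show that such deaths will in fact be dropped, since the sponsor may intend the narrower reading.

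The size cannot be derived from the documents. It depends on how many subjects die unassessed and on what counts as a clinical assessment for progression. The difference of 2 to 6 percentage points just before Week 24 is an illustration for 5 to 15 such deaths in 250 subjects with no other early event or censoring. It is not a forecast, and a Week 24 PFS rate is not a planned output. The primary complete remission rate and OS are unaffected. The point merits correction because the repair is small and the bias, if it arises, has a known direction.

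**What to change.** In SAP 10.1.1, replace the sentence with: If a subject has no post-baseline tumor or clinical assessment for progression and has not died, PFS is censored at first dose plus 1 day; a death without prior documented PD is a PFS event on the date of death. Then state what counts as a clinical assessment for progression, and in particular whether the routine examinations and blood counts before Week 24 do.

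At its next amendment, add the same condition, that the subject has not died, to protocol 8.1.2.2, and reconcile its enrollment-based date with the SAP's first-dose date. Protocol 8.1.2.2 also censors PFS when non-protocol CLL therapy starts before progression, a rule that SAP 10.1.1 does not repeat, so the new sentence should say which takes precedence for a death after such therapy.

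The SAP change costs a clause and a definition. If the intent was always to count these deaths, the clause leaves the intended analysis unchanged. A protocol amendment needs ethics committee approval (protocol 9.1), which is why that part should wait for the next one.
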